6.1.4. GCIG CA-125 Response

A GCIG CA-125 response is defined as a $\geq 50\%$ reduction in CA-125 levels from baseline. The response must be confirmed and maintained for at least 28 days. The CA-125 response will be conducted using the CA-125-Evaluable population. The date of response corresponds to the date when the CA-125 level is first reduced by 50%. The summary table for CA-125 will include the number (percentage) of patients in the CA-125-Evaluable population, and that number will then be used as the denominator for CA-125 response rate. The CA-125-Evaluable population is defined as all patients in the Safety population whose pretreatment sample is ≥ 2.0 times the upper limit of normal (ULN), within 2 weeks prior to first dose of MIRV, and who have at least 1 post-baseline CA-125 evaluation.

6.2. Primary Efficacy Outcome Analysis

The primary endpoint of ORR will be calculated based on the Efficacy Evaluable population, and its 95% exact CI will be estimated using the Clopper-Pearson method.

6.3. Secondary Efficacy Analyses

6.3.1. Key Secondary Efficacy Analysis

The key secondary endpoint of DOR will be summarized in patients with a confirmed BOR of CR or PR only.

The distribution of DOR will be summarized using the Kaplan-Meier method. DOR rates will be reported at 3-month intervals (e.g., 3 months, 6 months, etc.). Median DOR will be estimated from the 50th percentile of the corresponding Kaplan-Meier estimates. 95% CIs for the 3-month intervals and median DOR will also be provided.

6.3.2. Additional Secondary Efficacy Analyses

The following additional efficacy endpoints will be summarized.

- PFS
- OS
- TTR
- GCIG CA-125 response

PFS and OS will be summarized using the Efficacy Evaluable population. Their distribution will be estimated using the Kaplan-Meier method. PFS and OS rates will be reported at 3-month intervals (e.g., 3 months, 6 months, etc.). Median PFS and OS will be estimated using the 50th percentile of the corresponding Kaplan-Meier estimates. The 95% CI for the 3-month intervals and median times will also be provided. Additionally, the restricted mean survival time (RMST) will be reported at 3-month intervals (e.g., 3 months, 6 months, etc.).

The median follow-up time and its 95% CI will be estimated using reverse Kaplan-Meier method on OS.

GCIG CA-125 response rate will be calculated using the CA-125 Response-Evaluable population and its 95% exact CI will be estimated using the Clopper-Pearson method.

TTR will be summarized in patients with a confirmed BOR of CR or PR only with the simple summary statistics.

6.4. Efficacy Analysis on Subgroups of Patients

Efficacy endpoints (ORR, DOR, PFS, OS, and GCIG CA-125 response rate) will be analyzed with the following subgroups of patients:

- Number of prior lines of therapy.
- Prior exposure to Bevacizumab (yes vs no).

- Prior exposure to PARPi (yes vs no vs uncertain).
 - If a patient participated in a double-blind randomized trial comparing PARP inhibitor to placebo and the actual treatment was unknown, patient will be summarized under ‘uncertain’ category.
 - ‘yes’ and ‘uncertain’ may be combined as one group.
- Most recent PFI

The summaries for ORR and GCIG CA-125 response include the response rate and its 95% exact CI.

The summaries for time to event variables (DOR, PFS, and OS) include the number and percentage of events, median and its 95% CI.

6.5. Additional Sensitivity Analyses

Analysis of ORR, DOR, and PFS as assessed by BICR will be performed as sensitivity analysis using the same methods described in the previous sections.

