4. INVESTIGATIONAL PLAN

4.1. Study Design

4.1.1. Overview and Schema

This Phase 2 study is designed to evaluate the efficacy and safety of MIRV in patients with recurrent platinum-sensitive, high-grade serous EOC, primary peritoneal, or fallopian tube cancer, whose tumors express a high level of FR α . Patients will have had at least 2 prior lines of therapy. These will include at least 2 lines of platinum-containing therapy or 1 line with a documented platinum allergy. All patients will be, in the opinion of the Investigator, appropriate for non-platinum single-agent therapy for their next line of therapy. FR α positivity will be defined by the Ventana FOLR1 (FOLR1-2.1) CDx assay (Ventana FOLR1 Assay).

The study is designed to test the null hypothesis that the ORR is $\leq 28\%$ using an optimal Simon's two-stage design ([Simon 1989](#)) without a planned pause in enrollment given preliminary efficacy and established safety of MIRV. Approximately 75 patients will be enrolled so that a total of 69 patients will be efficacy evaluable.

Efficacy evaluable patients include those who have at least 1 measurable lesion (per RECIST v1.1) at baseline and received at least 1 dose of MIRV.

All patients will receive single-agent MIRV at 6 mg/kg AIBW ([Appendix D](#)) administered through IV infusion on Day 1 of every 3-week cycle (Q3W).

Computerized tomography (CT) or magnetic resonance imaging (MRI) scans will be collected for sensitivity analysis by BICR.

Patients will continue to receive MIRV until PD, unacceptable toxicity, withdrawal of consent, death, or until the Sponsor terminates the study (whichever comes first).

Tumor assessments, including radiological assessment by CT/MRI scans, will be performed at Screening and subsequently every 6 weeks (± 1 week) from Cycle 1 Day 1 (C1D1) for the first 36 weeks then every 12 weeks (± 3 weeks) until PD, death, the start of new anticancer therapy, or patient's withdrawal of consent, whichever occurs first.

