5.6. Discontinuation of the Patients from the Study or Study Treatment

5.6.1. End of Treatment

Patients will continue to receive MIRV until they present with PD per RECIST v1.1, as assessed by study Investigator, unacceptable toxicity, withdraw consent, or death, whichever comes first, or until the Sponsor terminates the study. Study treatment and/or participation in the study may be discontinued at any time at the discretion of the Investigator. The following may be reasons for the Investigator to remove a patient from the study drug:

- The patient suffers an intolerable AE
- Noncompliance, including failure to appear at one or more study visits
- The patient was erroneously included in the study

The reason for treatment discontinuation must be captured in the clinical trial database. Any AEs experienced up to the point of discontinuation and 30 days thereafter must be documented. All serious adverse events (SAEs), and those AEs assessed by the Investigator as at least possibly related to study drug should continue to be followed until they resolve or stabilize, whichever comes first. Patients will continue to be followed for OS, after discontinuing study drug ([Section 9.3.3](#)).

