7.13. Tumor Response Assessment

7.13.1. Radiological Imaging

Radiologic tumor evaluation by CT or MRI of chest, abdomen, and pelvis will be performed within 28 days before first dose of study drug and every 6 weeks (\pm 1 week) from C1D1 for the first 36 weeks on study and every 12 weeks (\pm 3 weeks) thereafter (Table 2). Patients who discontinue study treatment for reasons other than PD will continue with tumor assessments until documentation of PD or the start of a new anticancer therapy, whichever comes first. Prior to Week 36 (from C1D1), assessments should occur every 6 weeks (\pm 1 week) as allowed by local requirements but must occur at an interval of no more than 12 weeks. After Week 36, assessment will occur every 12 weeks (\pm 3 weeks) until documentation of PD or the start of new anticancer therapy. The same method of radiographic assessment used at Screening must be used at all subsequent radiographic evaluations. Copies of all imaging scans must be obtained and sent to a central imaging vendor designated by ImmunoGen as outlined in the Imaging Manual. The central imaging vendor will assess the quality of the images. The imaging vendor will be responsible for the formation and management of the BICR which will be used as a sensitivity analysis of ORR, DOR, and PFS by the Investigator.

Tumor response will be assessed by the Investigator using RECIST v1.1 (Eisenhauer 2009). Response as determined by the Investigator will be recorded in the clinical trial database.

The central imaging vendor will ensure that the central radiologists remain blinded to the local assessment from the Investigator and other unblinding information. This and all other imaging procedures will be documented in an independent review charter agreed upon between ImmunoGen and the imaging vendor before initiation of any BICR reviews.

Note: It is very important that the same method of radiologic assessment be used throughout the study and that the same lesions are followed.

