9.3.3. Survival Follow-up

All patients who discontinue MIRV for any reason will be followed for survival after PD as per Investigator, or after start of a new anticancer therapy. Survival status will be assessed every 3 months (\pm 1 month) until death, lost to follow-up, withdrawal of consent for survival follow-up, or until EOS, whichever comes first. Additional survival follow-up calls may occur periodically if needed.

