6.1.1.2. DOR

DOR is defined as the time from the date of the first response (CR or PR), whichever occurs first, to the date of PD or death from any cause, whichever occurs first. DOR is only defined for patients who have a confirmed BOR of CR or PR.

Per the BOR definition, patients with an overall response of CR or PR must have a repeat tumor assessment performed no less than 4 weeks after the criteria for response are first met. The first date at which a CR or PR response was noted will be used to calculate DOR, not the date of the confirmatory tumor assessment.

Patients who started a new anti-cancer therapy prior to documented PD or death will be censored at the last radiological assessment prior to initiation of new anti-cancer therapy. Patients who did not have PD or death or new anti-cancer therapy will be censored at the date of their last radiological assessment. Patients who had PD or death after missing 2 or more consecutive radiological assessments (PD or death date - last radiological assessment date +1 \geq 105 days or \geq 231 days if the assessment schedule has changed from every 6 weeks [+1 week] to every 12 weeks [+3 weeks] after Week 36 or after discontinuing from study treatment per local requirements). will be censored at the date of their last radiological assessment before the missing radiological assessment.

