6.1.2. PFS

PFS is defined as the time from the date of first dose of MIRV until the date of PD or death from any cause, whichever occurs first. PFS is defined based on radiological assessments and determined by the Investigator. Clinical progression is not considered a progression endpoint.

[Table 3](#) summarizes the rules to be used for PFS. When an analysis cutoff date is implemented, only data (deaths and radiological assessments) occurring on or prior to the cutoff date will be used for analysis.

Table 3: PFS Definitions

Situation	Date of PFS Event or Censoring	Outcome
No post-baseline radiological assessments, and patient did not die within 105 days of first dose	Date of first dose	Censored
No post-baseline radiological assessments, and patient died within 105 days of first dose	Date of death	Death
Death	Date of death	Death
Radiological Progression	Date of first radiological assessment indicating progression .	Progression
New anti-cancer therapy prior to PD or death (including palliative radiotherapy during study treatment)	Date of last radiological assessment prior to the start of the new anticancer therapy	Censored
No death or PD	Date of last radiological assessment	Censored
PD or death after missing 2 or more consecutive radiological assessments (PD or death date - last radiological assessment date +1 \geq 105 days or \geq 231 days if the assessment schedule has changed from every 6 weeks [+1 week] to every 12 weeks [+3 weeks] after Week 36 or after discontinuing from study treatment per local requirements).	Date of last adequate radiological assessment showing no PD	Censored

6.1.3. OS

OS is defined as the time from the date of first dose until the date of death from any cause.

Patients who are alive or lost to follow-up at the analysis are censored at the last known date at which they were known to be alive.

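### BICR DOR and PFS normally censor a patient at a progression that only the Investigator calls, which probably biases both curves upward by an amount the documents do not determine

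*SAP*

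**What the plan says.** **When scanning ends.** Protocol 4.1.1 schedules tumor assessments "until PD, death, the start of new anticancer therapy, or patient's withdrawal of consent, whichever occurs first". That sentence does not name the assessor, but the surrounding sections do. Protocol 7.13.1 gives response assessment to the Investigator. Protocol 5.6.1 states: "Patients will continue to receive MIRV until they present with PD per RECIST v1.1, as assessed by study Investigator". Scans after stopping treatment are planned only for patients who stop for a reason other than PD (Protocol 4.1.1, 7.13.1, 9.3.2). The others are "followed for survival after PD as per Investigator, or after start of a new anticancer therapy" (Protocol 9.3.3).

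**Role of BICR.** Protocol 7.13.1 describes a "BICR which will be used as a sensitivity analysis of ORR, DOR, and PFS by the Investigator". BICR reads the scans that were collected. It has no part in deciding when scanning or treatment stops.

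**How BICR DOR and PFS are censored.** SAP 6.5 applies "as assessed by BICR will be performed as sensitivity analysis using the same methods described in the previous sections". The rules carried over are:
- DOR (SAP 6.1.1.2): "Patients who did not have PD or death or new anti-cancer therapy will be censored at the date of their last radiological assessment".
- DOR, new therapy first (SAP 6.1.1.2): "Patients who started a new anti-cancer therapy prior to documented PD or death will be censored at the last radiological assessment" before that therapy.
- PFS, new therapy first (SAP 6.1.2, Table 3): "Date of last radiological assessment prior to the start of the new anticancer therapy".
- Both: a PD or death that follows two or more missed assessments (105 days or more, or 231 days or more on the 12-week schedule) is censored.

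The SAP has no rule for Investigator PD without BICR PD, no analysis that counts it as an event, and no planned summary of disagreement between the two assessments.

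**The concern.** Kaplan-Meier assumes that a censored patient has the same future risk as those still under observation. Here the censoring is triggered by a reader of the same images judging that the disease has progressed. Once that happens there are no more scans, so a later BICR PD cannot be seen. The DOR update 12 months after the primary analysis (Protocol 10.3.2) cannot recover it.

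The trial is single-arm and open-label, and its key secondary endpoint, DOR, is Investigator-assessed. BICR is the only planned look at DOR and PFS by a different reader. If its curves are lifted because events could not be observed, they are a weaker check on the Investigator result than they appear to be.

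**Working it through.** **1. Following one patient through the rules.** The Investigator calls PD at a scan and BICR does not. Treatment and scans stop. In the BICR analysis she has no PD.
- If she starts new therapy, she is censored at the last scan before it, normally the scan in question.
- If she starts none and is alive, she is censored at her last scan, the same one.
- If she dies without new therapy inside the 105- or 231-day window, the death counts as an event. This is the only exception.

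In the Investigator analysis the same patient is an event at that scan.

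**2. No plan figure to reproduce.** The documents give no figure for BICR DOR or PFS, for the share of Investigator PDs that BICR does not call (d), or for the lag to a later BICR PD. Both inputs are therefore assumptions and are shown over a range.

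**3. Illustration for PFS.** From the documents: 69 evaluable patients and scans every 6 weeks to Week 36, then every 12 weeks. Assumed: exponential PFS with median 7 months, follow-up of 9 to 21 months, d of 10%, 20% or 30%, and post-PD deaths ignored.

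Nine months falls between the Week 36 and Week 48 scans, so the 9-month rate is the level of the curve after Week 36.
- Week 36 = 36 × 7 / 30.4375 = 8.28 months.
- With Investigator PD as the event: exp(−ln 2 × 8.28 / 7) = 0.44.
- As planned, a share d of events becomes censoring at the same scan, so the curve is close to 0.4405^(1−d): 0.4405^0.9 = 0.478, 0.4405^0.8 = 0.519, 0.4405^0.7 = 0.563. Simulation gives 0.480, 0.525 and 0.568.

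These planned values do not depend on the lag. What changes with the lag is the rate that continued scanning would have shown.

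| If scanning had continued, BICR PD would come | Excess of planned 9-month BICR PFS (d = 10/20/30%) | Shortfall of the earliest-of event |
|---|---|---|
| at the next scan | +3 / +7 / +11 points | 1 to 2 points |
| three scans later on average | +2 / +4 / +6 points | about 2 to 6 points |
| at the baseline hazard | about 1 point or less | about 4 to 12 points |

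For the first row, continued scanning gives 0.448, 0.453 and 0.460. The excess is 0.480 − 0.448 = 0.032, 0.525 − 0.453 = 0.072 and 0.568 − 0.460 = 0.108. Against a standard error of about 0.06 that is 0.5, 1.2 and 1.8 standard errors.

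**4. Second illustration, with post-PD deaths.** This run had latent BICR medians of 24 or 35 weeks, Investigator PD one or two scans ahead of BICR in 10% to 40% of patients, 80% starting new therapy, and deaths without new therapy inside 105 days counted as events. The 52-week BICR event-free rate rose by about 2 to 14 points (from about 0.25 to 0.27–0.39, and from about 0.39 to 0.41–0.53). When Investigator-only PD was unrelated to later BICR PD, the change was about 1 point or less. Counting Investigator PD as an event in the early-call settings gave 0.20–0.24 and 0.33–0.38, at or below the continued-scan rate.

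**5. DOR.** Not simulated. DOR covers confirmed responders only: at the design alternative, 0.48 × 69 ≈ 33 patients. For a rate near 45% the standard error is about √(0.45 × 0.55 / 33) = 0.087, against √(0.45 × 0.55 / 69) = 0.060 for PFS.

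**The case against.** The strongest reply is that the size rests on the assumed lag. BICR PD at the very next scan is close to the most informative case possible. If Investigator-only PD says nothing about later BICR PD, the shift almost disappears. This stands: the documents support a likely direction, not a size. Some upward shift remains the reasonable expectation, because both assessments rest on the same scans and a patient read as progressed by one is unlikely to be at merely average risk by the other.

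Several other limits also stand:
- In the first illustration the BICR median goes from 8.3 to 11.0 months at d of 20% or more with a next-scan lag. A reader might take this as the effect size. It is one step of the scan grid, Week 36 to Week 48, taken because the curve crosses 50%. At d of 10% the median does not move.
- BICR may also call PD before the Investigator does. Those dates count as BICR events and pull the BICR curve down. This was not modelled, so the net comparison of BICR with Investigator results is unknown.
- Counting Investigator PD as an event is not a correction. With longer lags it is too low by about as much as, or more than, the planned analysis is too high, and it brings the open-label Investigator call back into the BICR endpoint.
- BICR is labelled a sensitivity analysis, and SAP 4.11.2 plans no formal test of secondary endpoints. The independent review charter named in Protocol 7.13.1 is not among the documents. It may govern the reads, but the censoring rules are set in the SAP.

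**Conclusion.** The point holds in a limited form. As written, a patient with Investigator PD that BICR does not call is normally censored at that scan in BICR DOR and PFS, and nothing else in the plan counts or reports her. The BICR curves are likely biased upward. For 9-month PFS under the assumptions shown, the excess ranges from about 1 point or less to about 11 points, depending on discordance from 10% to 30% and on the lag. The effect on DOR is expected to run the same way but has not been quantified.

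A reader might infer that the BICR results are certain to be inflated, or that they will match or exceed the Investigator results for this reason alone. The documents do not support either: they give no discordance rate or lag, and disagreement can run in both directions. Nor does the point touch the primary ORR test or Investigator-assessed DOR and PFS.

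**What to change.** In SAP 6.5, keep the planned BICR analyses and add:
1. For BICR DOR and BICR PFS, a companion Kaplan-Meier analysis with the event at the earliest of BICR PD, Investigator PD or death, labelled as a conservative lower bound.
2. The number of patients censored in each BICR analysis who had Investigator PD.
3. A table of Investigator/BICR concordance on PD status and PD date, in both directions.
4. A sentence stating that the planned BICR curves may be subject to informative censoring at Investigator PD.

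The cost is SAP wording, one more Kaplan-Meier run per endpoint, and one table, all on data already collected. No further scans or reads are needed. SAP 2.1 allows changes before final database lock. The companion estimate will be shorter, may overcorrect, and is not independent of the Investigator's PD calls, so it bounds the BICR result and does not replace it.

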6.6. Other Efficacy-related Summaries

- New anti-cancer therapy will be summarized
- Type of new anti-cancer therapy include:
 - Taxanes.
 - Topotecan.
 - Platinum compounds.
 - Anthracyclines.
 - Chemotherapy (other).
 - Bevacizumab.
 - Hormonal therapy.
 - Kinase inhibitors.
 - PARP inhibitors.
 - PD-1/PD-L1 inhibitors.
 - Other.

7. SAFETY ANALYSES

The main safety summary tables will use data from the Safety population. Listings will be provided for patients in the Safety population.

7.1. Exposure

Summary tables will be provided with the following information.

Exposure to MIRV will be summarized with descriptive statistics for the number of doses received, duration of dosing (weeks, months), total cumulative dose (mg), absolute dose intensity (mg/kg/dose, calculated as total cumulative dose [mg])/number of valid drug administration records /AIBW [kg]).

Duration of dosing in weeks = (the last dose date-the first dose date +21) /7

Duration of dosing in months = (the last dose date-the first dose date +21) /30.4375

A listing will be provided with the information from all MIRV administration case report forms (CRFs) over the treatment period.

7.2. AEs

AEs will be documented on the AE CRF and monitored continuously throughout the study from the time of informed consent until 30 days after the patient's last MIRV or until the event has resolved, stabilized, or returned to baseline. AEs attributed to study procedures, including those events that occur prior to the first dose, should also be documented on the AE CRF.

AE data are available to ImmunoGen from 2 sources, the clinical database and the serious adverse event (SAE) forms. While reconciliation will be performed, the production of data summaries and listings will be based on the data collected on the clinical database.

Pre-treatment AEs are defined as AEs with an onset date prior to the first dose of MIRV. TEAEs are defined as AEs with an onset date on or after the first dose of MIRV, and within 30 days of the last dose of MIRV or prior to the start of a new anti-cancer treatment, whichever occurs first. Medical history conditions that exist before the initiation of MIRV but worsen in severity during the study will also be recorded on the AE CRF as an AE and will be included as treatment-emergent in the summary tables and listings.

The adverse events will be coded using MedDRA (Version 24.0 or later), associating lower-level terms with PT and SOC by the primary hierarchy. The tables will display the counts and percentages of patients who reported at least 1 TEAE in each SOC represented in the AE data. Within each SOC, the tables will display the counts and percentages of patients reporting at least 1 TEAE as designated by the PT.

AEs are graded using CTCAE Version 5.0. AE summaries may include summaries for all AEs and by the maximum CTCAE grade for the item being summarized (ie, SOC or PT). In these cases, the outputs will include a row for All Grades as well as rows for the 5 potential CTCAE grades, Grade 1 (Mild), Grade 2 (Moderate), Grade 3 (Severe), Grade 4 (Life threatening or disabling), or Grade 5 (Death). AEs missing a severity grade will not be included in the Grade 1-5 rows of the tables. An AE reported by a patient more than once will be represented in the most severe category TEAEs will be categorized as MIRV-related if "Possibly Related", "Probably Related", or "Definitely Related" is selected by Investigator. AEs missing relationship to MIRV will be included in the Related TEAE tables.

The following AE summary tables will be produced.

- An overall summary of TEAEs
- All TEAEs by SOC and PT
- TEAEs by PT
- Serious TEAEs by SOC and PT
- Grade 3 or higher TEAEs by SOC and PT
- TEAEs leading to drug withdrawal by SOC and PT. This subset includes TEAEs with an action taken of drug permanently discontinued.
- Related TEAEs leading to drug withdrawal by SOC and PT. This subset includes TEAEs related to MIRV with an action taken of drug permanently discontinued.
- TEAEs related to MIRV by SOC and PT.
- Serious, related TEAEs by SOC and PT.
- TEAEs leading to dose modifications (dose reduction, dose held, or dose delay) by SOC and PT.
- Related TEAEs leading to dose modification (dose reduction, dose held, or dose delay) by SOC and PT.
- Deaths on study treatment or within 30 days of the last dose. This table includes all deaths during study treatment or within 30 days of the last dose, regardless of cause of death.
- TEAEs leading to death. This table includes all TEAEs with CTCAE Grade 5.
- Related TEAEs leading to death. This table includes all TEAEs related to MIRV with CTCAE Grade 5.

The following listings will be produced:

- All AEs, sorted chronologically by patient. This listing includes SOC, PT, onset and end dates, and other relevant information.
- Serious TEAEs, sorted chronologically within patient.
- TEAEs leading to drug withdrawal. This subset includes TEAEs with an action taken of drug permanently discontinued.
- TEAEs leading to dose reduction.
- TEAEs resulting in death. This listing includes TEAEs with a CTCAE grade of Grade 5 (death).
- All deaths, with an indication of whether the death occurred on study or within 30 days of the last dose.

The following groupings of TEAEs will be generated as part of the focused analysis of safety:

- Ocular TEAEs.

- A list of PTs for ocular AEs will be provided and finalized by the Sponsor before the final database lock.
- Peripheral neuropathy TEAEs.
 - A list of PTs for peripheral neuropathy AEs will be provided and finalized by the Sponsor before the final database lock.
- Pneumonitis

Additionally, tables will be produced which contains the following.

- TEAEs by PT and maximum CTCAE grade
- Time to first onset of TEAEs.
- Action taken of TEAEs.
- Resolution of TEAEs

